#### **6.5.6 Bone Safety Monitoring**

Measurement of LS-BMD Z-score at Visits 5 and 8 (months 6 and 12) will be subject to monitoring from the central imaging lab for the detection of excessive changes in BMD. Repeat scans may be requested if technical factors are suspected to be involved. The investigator will be notified in the case of an absolute change in LS-BMD greater than -0.5 compared with screening at the Month 6 or 12 visits or an absolute increase of LS-BMD of greater than +2.0. In either event, the investigator should further assess the patient for secondary causes (e.g. underlying disease). If it is in the best interests of the patient to discontinue the study, discontinuation procedures should be followed as described in [Section 5.6.2](#)

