To evaluate between-treatment differences for the proportion of patients with new vertebral fractures at Month 12 relative to baseline.	Title: Incidence of new vertebral fractures Unit of measure: number and percentage of new vertebral fractures Description: See Section 6.4.1 Time frame: baseline, and 12 months	Section 9.5.1.4
To evaluate the between-treatment differences for change in vertebral morphometry at Month 12 relative to baseline.	Title: Change in vertebral morphometry Description: Quantitative morphometry will be performed by a central reader (see Section 6.4.1 ) Time frame: baseline, and 12 months	Section 9.5.1.5
To evaluate the between-treatment differences for change in pain using the Faces Pain Scale-Revised (FPS-R) at Months 3, 6, 9 and 12 relative to baseline.	Title: Change in pain scale Description: Children will select the face that best fits their pain ( Appendix 4 ) Time frame: baseline, 3, 6, 9 and 12 months	Section 9.5.1.7
To evaluate the between-treatment differences for change in 2nd metacarpal cortical width at Month 12 relative to baseline.	Title: Change in metacarpal cortical width Description: The X-ray Manual provides instructions on the technique. Skeletal bone age will be determined as described in the Imaging Charter Time frame: baseline and 12 months	Section 9.5.1.6
To measure urinary concentration of zoledronic acid at Month 12.	Title: Pharmacokinetics Unit of measure: ng/mL Description: urine will be collected overnight or for at least 4 waking hours from all patients able to provide specimens Time frame: 12 months	Section 9.5.3
The safety objective is to demonstrate that zoledronic acid is safe for the treatment of osteoporotic children treated with glucocorticoids through the monitoring of relevant clinical and laboratory safety parameters	Title: Safety: adverse events, laboratory evaluations and vital signs Description: adverse events will be collected from the first infusion (Visit 2), blood and urine samples, including renal monitoring will be collected (See Section 6.5 ). Also bone safety (change in LS-BMD) is monitored at months 6 and 12. Time frame: baseline through 12 months	Section 9.5.2

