### **5.6.2 Discontinuation of Study Treatment**

Discontinuation of study treatment for a patient occurs when study drug is stopped earlier than the protocol planned duration i.e. before Visit 5, Month 6, and can be initiated by either the patient or the investigator.

The investigator must discontinue study treatment for a given patient if he/she believes that continuation would negatively impact the risk/benefit of trial participation.

Study treatment must be discontinued under the following circumstances:

- Patient's wish
- Pregnancy (see [Section 6.5.5](#) and [Section 7.4](#))
- Use of prohibited treatment as per recommendations in [Section 5.5.8](#)
- Any situation in which study participation might result in a safety risk to the patient
- Emergence of the following adverse events:
  - Osteonecrosis of the jaw
  - Renal failure
  - Any laboratory abnormalities that in the judgment of the investigator, taking into consideration the patient's overall status, prevents the patient from continuing participation in the study

If discontinuation of study treatment occurs, the patient should NOT be considered withdrawn from the study. The patient should return to the clinic as soon as possible, after discontinuation of study drug, for a study treatment discontinuation visit. Treatment discontinuation visit assessments detailed in Visit 8, Month 12 in [Table 6-1](#) should be completed and recorded in the CRF. The investigator must determine the primary reason for the patient's premature discontinuation of study treatment and record this information on the Dosage administration record CRF.

After study treatment discontinuation, at a minimum, in abbreviated visits, the following data should to be collected at clinic visits or via telephone visits:

- new / concomitant treatments
- adverse events/serious adverse events

If the patient cannot or is unwilling to attend any visit(s), the site staff should maintain regular telephone contact with the patient, or with a person pre-designated by the patient, preferably according to the study visit schedule.

The investigator must contact the IRT to register the patient's discontinuation from study treatment.

If study drug discontinuation occurs because treatment code has been broken, please refer to [Section 5.5.9](#)

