#### **6.5.7 Appropriateness of safety measurements**

Safety assessments consist of monitoring and recording of all adverse events and serious adverse events, including those known to be associated with bisphosphonate use; renal function (serum creatinine and GFR), regular monitoring of hematology, blood chemistry and urine values, regular measurement of vital signs and the performance of physical examinations including oral examinations for exposed bone. An oral examination of the gums and roof of the mouth, will be performed as part of the physical examination at screening, randomization, Month 6 and Month 12 visits to assess for signs of ONJ. ONJ is characterized by exposed bone in the maxillofacial area that occurs in association with dental surgery, or occurs spontaneously, with no evidence of healing. See [Section 3.6](#).

[figure not shown]
Tanner staging assesses the sexual maturity of the patient and is important to indicate child-bearing potential in girls as these girls will require pregnancy tests before each infusion.

Vitamin D (25-hydroxy-D) and calcium will be measured at Visit 1 to ensure that all patients have adequate vitamin D and calcium levels at study entry, as a precaution to minimize the risk of developing hypocalcemia with the first zoledronic acid administration. In addition, ionized calcium will be monitored locally, before the first infusion to ensure that the patients have normal serum calcium level. Families will be counselled on the importance of a diet rich in calcium and vitamin D, and supplements recommended based at the investigators discretion.

Bone safety is monitored by the central imaging laboratory via DXA at Month 6 and 12. In case of excessive change in BMD Z-scores compared with screening, the investigator will be alerted.

The safety assessments selected are standard for this indication/patient population.

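### Protocol 6.5.6 states its bone-safety alert limits on LS-BMD rather than LS-BMD Z-score, and the lower limit points the wrong way if read literally

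*Protocol*

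**What the plan says.** Section 6.5.6 of the protocol opens on the Z-score scale: "Measurement of LS-BMD Z-score at Visits 5 and 8 (months 6 and 12) will be subject to monitoring from the central imaging lab". It then sets two triggers for telling the investigator. The lower one is "The investigator will be notified in the case of an absolute change in LS-BMD greater than -0.5 compared with screening", at Month 6 or Month 12. The upper one is "an absolute increase of LS-BMD of greater than +2.0". Neither trigger mentions Z-score or carries a unit.

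Two other places describe the same monitoring. Section 6.5.7 uses the Z-score: "In case of excessive change in BMD Z-scores compared with screening, the investigator will be alerted". The safety row of Table 2-1 does not: "Also bone safety (change in LS-BMD) is monitored at months 6 and 12". That row contains no limit.

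After an alert, the investigator looks for secondary causes. Stopping is optional: "If it is in the best interests of the patient to discontinue the study, discontinuation procedures should be followed as described in" Section 5.6.2. That section concerns study drug stopped ahead of plan, "i.e. before Visit 5, Month 6, and can be initiated by either the patient or the investigator". It adds: "If discontinuation of study treatment occurs, the patient should NOT be considered withdrawn from the study".

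**The concern.** An alert limit is a decision rule. It should give the scale, the direction and the size of the change, so that two people applying it to the same scan reach the same answer. Section 6.5.6 leaves the scale to be inferred, and its lower limit gives the wrong direction if the words are taken as they stand. A number greater than -0.5 can be -0.3, 0 or +1.2; it cannot be -0.8, which is the kind of result the rule exists to catch. Reading 'absolute' as the size of the change in either direction gives a third rule.

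What is at stake is a safety notice about a child who is losing bone. Under the literal rule that child triggers no notice, while most children who are stable or gaining do. There is also a smaller wording matter. Section 6.5.6 speaks of leaving the study, but the section it points to is about stopping study drug.

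**Working it through.** **Inputs.** Protocol 9.8 (repeated in the SAP under Determination of sample size): mean 12-month change in LS-BMD Z-score of 0 on placebo and 0.63 on zoledronic acid, common SD 0.93, two-sided 0.05, power 85%, 82 evaluable, 46 per arm randomized. The changes are taken as normally distributed, which is an assumption.

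**The plan's own figure.** The alert limits have no derivation to reproduce, so the check is that 0.63 and 0.93 are the values behind the sample size.
- Normal approximation: n per arm = 2 × (1.960 + 1.036)² × 0.93² / 0.63² = 39.1, so 40.
- Noncentral t: power is 84.9% at 40 per arm and 85.8% at 41, so 41 per arm, or 82.
- Dropout: 82 / 0.90 = 91.1, so 92. The figures reproduce.

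**Three readings of the lower limit at Month 12.** Φ is the standard normal distribution function.
- Intended, change < -0.5: placebo Φ(-0.5/0.93) = Φ(-0.538) = 0.295; active Φ((-0.5 - 0.63)/0.93) = Φ(-1.215) = 0.112.
- Literal, change > -0.5: the complements, 0.705 and 0.888.
- Size of change above 0.5 in either direction: placebo 2 × 0.295 = 0.591 (before rounding); active 0.112 + [1 - Φ((0.5 - 0.63)/0.93)] = 0.112 + 0.556 = 0.668.

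| Reading of lower limit | Placebo | Active | Children of 92 |
|---|---|---|---|
| Fall of more than 0.5 (intended) | 29.5% | 11.2% | 46 × (0.295 + 0.112) ≈ 19 |
| Change greater than -0.5 (literal) | 70.5% | 88.8% | 46 × (0.705 + 0.888) ≈ 73 |
| Size of change above 0.5 | 59.1% | 66.8% | 46 × (0.591 + 0.668) ≈ 58 |

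The literal reading also reverses the arms: the intended rule flags more placebo children, the literal rule more active children.

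**Adding the upper limit.** A rise above 2.0 has probability 1 - Φ(2.0/0.93) = 0.016 on placebo and 1 - Φ(1.37/0.93) = 0.070 on active. Both intended limits together flag 31.1% and 18.3%, about 14 and 8 of 46. Under the other two readings the +2.0 limit adds nothing, because any rise above 2.0 is already flagged.

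**Month 6.** The documents give no Month 6 mean or SD. Assume an active mean of 0.315 (half the planned effect), placebo 0, and SD between 0.5 and 0.93.

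| Assumed SD | Intended lower limit, placebo / active | Literal, placebo / active |
|---|---|---|
| 0.5 | 15.9% / 5.2% | 84.1% / 94.8% |
| 0.93 | 29.5% / 19.0% | 70.5% / 81.0% |

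The contrast is the same across this range. A reading in g/cm² was not quantified, because the documents give no LS-BMD values in that unit.

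**The cross-reference.** Month 6 DXA and the second, last infusion both fall at Visit 5 (Table 6-1). If the central read comes back before that infusion, Section 5.6.2 applies directly. If it comes back later, there is no study drug left to stop, and what remains is whether the child stays in the study. Section 6 covers early departure for any reason. Section 5.6.2 calls for the Visit 8 assessments, DXA included, at the discontinuation visit; after that its list of minimum data names treatments and adverse events only. The general Month 12 DXA requirement stands elsewhere: Section 3.6 and Section 6.4.3 apply DXA at Months 6 and 12 to all patients, and Section 6 asks that every visit be kept. The 5.6.2 list does not repeat this, nor does it cancel it.

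**The case against.** The strongest reply is that nobody would apply the literal rule. The sentence follows directly on one about Z-score monitoring, 6.5.7 names Z-scores, and 'absolute' is naturally read as a difference rather than a percentage. The pair of limits settles direction: a separate +2.0 trigger makes sense only if the first trigger concerns falls. The rule is applied by the central imaging laboratory, working from a DXA manual and Imaging Charter that may be worded correctly, and the investigator only receives a notice. On this view, 73 of 92 describes a reading that nobody intended.

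Most of that stands, and it is why the point is minor. It does not make the sentence right. The protocol's threshold should agree with whatever the manuals say without being reinterpreted first.

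A reader might go further and infer that a child who stops after a Month 6 alert has no required Month 12 DXA, so that carrying the Month 6 value forward biases the primary analysis. The documents do not support this. The all-patient DXA provisions in 3.6 and 6.4.3 and the visit rule in 6 remain in force, 5.6.2 keeps the child in the study and already requires a scan at discontinuation, and its follow-up list is a stated minimum. The alert does not oblige anyone to stop. A bias estimate would need a Month 6 mean and SD, a Month 6 to 12 correlation and a stopping rate, none of which the documents give; even its sign would depend on them. Nor is a further X-ray requirement justified: it would do nothing for the DXA endpoint, and Section 3.6 restricts repeat imaging in these children.

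**Conclusion.** The lower alert limit in 6.5.6 is wrong as written: the scale is missing and the direction is reversed on a literal reading. The intent is recoverable, so this is a minor correction to a safety rule and not evidence that the monitoring was carried out wrongly. The size of the discrepancy, 29.5% and 11.2% against 70.5% and 88.8%, rests on the plan's Month 12 means and SD and on normality. It measures how far apart the readings are; it does not predict how many alerts were issued. Sample size and the primary analysis are unaffected.

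The mismatch between leaving the study (6.5.6) and stopping drug (5.6.2) is a secondary matter of wording, worth one clarifying clause.

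**What to change.** 1. In 6.5.6, state the triggers as: *a decrease of more than 0.5 or an increase of more than 2.0 in LS-BMD Z-score from screening, at Month 6 or Month 12*.
2. In the bone-safety entry of Table 2-1, write *LS-BMD Z-score*. Section 6.5.7 already uses the Z-score. Check that the DXA manual and Imaging Charter agree.
3. In 6.5.6 or 5.6.2, add a clause that a child who stops study drug but has not left the study keeps the Month 12 DXA already scheduled. Leave the decision to stop with the investigator, as now.

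The cost is a few words of protocol text. The clause in item 3 confirms an existing scheduled scan and creates no new requirement. The sample size, the analysis and the X-ray schedule stay as they are.

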#### **6.5.7 Appropriateness of safety measurements**

Safety assessments consist of monitoring and recording of all adverse events and serious adverse events, including those known to be associated with bisphosphonate use; renal function (serum creatinine and GFR), regular monitoring of hematology, blood chemistry and urine values, regular measurement of vital signs and the performance of physical examinations including oral examinations for exposed bone. An oral examination of the gums and roof of the mouth, will be performed as part of the physical examination at screening, randomization, Month 6 and Month 12 visits to assess for signs of ONJ. ONJ is characterized by exposed bone in the maxillofacial area that occurs in association with dental surgery, or occurs spontaneously, with no evidence of healing. See [Section 3.6](#).

[figure not shown]
Tanner staging assesses the sexual maturity of the patient and is important to indicate child-bearing potential in girls as these girls will require pregnancy tests before each infusion.

Vitamin D (25-hydroxy-D) and calcium will be measured at Visit 1 to ensure that all patients have adequate vitamin D and calcium levels at study entry, as a precaution to minimize the risk of developing hypocalcemia with the first zoledronic acid administration. In addition, ionized calcium will be monitored locally, before the first infusion to ensure that the patients have normal serum calcium level. Families will be counselled on the importance of a diet rich in calcium and vitamin D, and supplements recommended based at the investigators discretion.

Bone safety is monitored by the central imaging laboratory via DXA at Month 6 and 12. In case of excessive change in BMD Z-scores compared with screening, the investigator will be alerted.

The safety assessments selected are standard for this indication/patient population.

## **6.6 Other assessments**

### 6.6.3 Pharmacokinetics

Further details on sample collection, numbering, processing and shipment can be found in the Laboratory Manual

Urine will be collected into a polypropylene container during at least a 4-hour sampling period at Visit 8 (Month 12). The first morning sample may be used if the time of the previous night's bladder voiding is recorded, otherwise it should be discarded (see Laboratory Manual for further details).

All samples will be given a unique sample number. The actual sample collection date and time will be entered on the PK urine collection page of the eCRF.

#### Pharmacokinetic analytical method

Zoledronic acid will be determined in urine by a validated radio-immunoassay method. The Lower Limit of Quantification (LLOQ) is 10 ng/mL. Concentrations below the LLOQ will be reported as "zero" and missing data will be labeled as such in the Bioanalytical Data Report.

#### Pharmacokinetics parameters

Aet1-t2 will be calculated as  $A_{et1-t2} = \text{urine volume (t1-t2)} \times \text{urine concentration}$ .

## 7 Safety monitoring

### 7.1 Adverse events

An adverse event (AE) is any untoward medical occurrence (e.g., any unfavorable and unintended sign [including abnormal laboratory findings], symptom or disease) in a subject or clinical investigation subject *after providing written informed consent* for participation in the study until the end of study visit. Therefore, an AE may or may not be temporally or causally associated with the use of a medicinal (investigational) product.

In addition, all reports of intentional misuse and abuse of the product are also considered an adverse event irrespective if a clinical event has occurred.

In this protocol, due to the long screening period (at least 4 weeks), although SAEs are collected from signing the informed consent, the AE page of the eCRF is only completed from the first day of study drug. In the case of randomized patients only, any events that occur prior to receiving study treatment, should be recorded in the eCRF as Medical History.

The occurrence of adverse events must be sought by non-directive questioning of the patient at each visit during the study. Adverse events also may be detected when they are volunteered by the patient during or between visits or through physical examination findings, laboratory test findings, or other assessments.

Abnormal laboratory values or test results constitute adverse events only if they fulfill at least one of the following criteria:

- they induce clinical signs or symptoms,
- they are considered clinically significant,
- they require therapy.

Clinically significant abnormal laboratory values or test results must be identified through a review of values outside of normal ranges/clinically notable ranges, significant changes from baseline or the previous visit, or values which are considered to be non-typical in patient with underlying disease. Investigators have the responsibility for managing the safety of individual patient and identifying adverse events. Alert ranges for laboratory and other test abnormalities are included in [Appendix 1](#).

Adverse events must be recorded in the Adverse Events CRF under the signs, symptoms or diagnosis associated with them, accompanied by the following information:

- the severity grade
  - mild: usually transient in nature and generally not interfering with normal activities
  - moderate: sufficiently discomforting to interfere with normal activities
  - severe: prevents normal activities

There may be cases where a severe AE that is life-threatening may not necessarily be an SAE (e.g. certain laboratory abnormalities in the absence of meeting other seriousness criteria).

- its relationship to the
  - study treatment (no/yes), or
  - other treatment (no/yes). or
  - both or indistinguishable
- its duration (start and end dates) or if the event is ongoing an outcome of not recovered/not resolved must be reported.
- whether it constitutes a serious adverse event (SAE - See [Section 7.2](#) for definition of SAE)
- action taken regarding investigational treatment

All adverse events must be treated appropriately. Treatment may include one or more of the following:

- no action taken (e.g. further observation only)
- investigational treatment dosage adjusted/temporarily interrupted

- investigational treatment permanently discontinued due to this adverse event
- concomitant medication given
- non-drug therapy given
- patient hospitalized/patient's hospitalization prolonged (see [Section 7.2](#) for definition of SAE)
- its outcome (not recovered/not resolved; recovered/resolved; recovering/resolving, recovered/resolved with sequelae; fatal; or unknown)

Once an adverse event is detected, it must be followed until its resolution or until it is judged to be permanent, and assessment must be made at each visit (or more frequently, if necessary) of any changes in severity, the suspected relationship to the study drug, the interventions required to treat it, and the outcome.

Information about common side effects already known about the investigational drug can be found in the Investigator Brochure (IB). This information will be included in the patient informed consent and should be discussed with the patient during the study as needed. Any new information regarding the safety profile of the medicinal product that is identified between IB updates will be communicated as appropriate, for example, via an Investigator Notification or an Aggregate Safety Finding. New information might require an update to the informed consent and has then to be discussed with the patient.

The investigator must also instruct each patient to report any new adverse event (beyond the protocol observation period) that the patient, or the patient's personal physician, believes might reasonably be related to study treatment. This information must be recorded in the investigator's source documents; however, if the AE meets the criteria of an SAE, it must be reported to Novartis.

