## **7.2 Serious adverse events**

### **7.2.1 Definition of SAE**

An SAE is defined as any adverse event [appearance of (or worsening of any pre-existing)] undesirable sign(s), symptom(s) or medical condition(s) which meets any one of the following criteria:

- is fatal or life-threatening
- results in persistent or significant disability/incapacity
- constitutes a congenital anomaly/birth defect
- requires inpatient hospitalization or prolongation of existing hospitalization, unless hospitalization is for:
  - routine treatment or monitoring of the studied indication, not associated with any deterioration in condition (specify what this includes)
  - elective or pre-planned treatment for a pre-existing condition that is unrelated to the indication under study and has not worsened since signing the informed consent
  - treatment on an emergency outpatient basis for an event not fulfilling any of the definitions of a SAE given above and not resulting in hospital admission

- social reasons and respite care in the absence of any deterioration in the patient's general condition
- is medically significant, e.g. defined as an event that jeopardizes the patient or may require medical or surgical intervention.

All malignant neoplasms will be assessed as serious under “medically significant” if other seriousness criteria are not met.

Life-threatening in the context of a SAE refers to a reaction in which the patient was at risk of death at the time of the reaction; it does not refer to a reaction that hypothetically might have caused death if it were more severe (see Annex IV, ICH-E2D Guideline).

Medical and scientific judgment should be exercised in deciding whether other situations should be considered serious reactions, such as important medical events that might not be immediately life threatening or result in death or hospitalization but might jeopardize the patient or might require intervention to prevent one of the other outcomes listed above. Examples of such events are intensive treatment in an emergency room or at home for allergic bronchospasm, blood dyscrasias or convulsions that do not result in hospitalization or development of dependency or abuse (see Annex IV, ICH-E2D Guideline).

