### **7.2.2 SAE reporting**

To ensure patient safety, every SAE, regardless of causality, occurring after the patient has provided informed consent and until 30 days after the last study visit must be reported to Novartis within 24 hours of learning of its occurrence. Any SAEs experienced after the 30 day period after the last study visit should only be reported to Novartis if the investigator suspects a causal relationship to study treatment.

All follow-up information for the SAE including information on complications, progression of the initial SAE and recurrent episodes must be reported as follow-up to the original episode within 24 hours of the investigator receiving the follow-up information. An SAE occurring at a different time interval or otherwise considered completely unrelated to a previously reported one must be reported separately as a new event.

Information about all SAEs (*either initial or follow up information*) is collected and recorded on the paper Serious Adverse Event Report Form. The investigator must assess the relationship to *each specific component of study treatment (if study treatment consists of several components)* complete the SAE Report Form in English, and send the completed, signed form by fax within 24 hours after awareness of the SAE to the local Novartis Drug Safety and Epidemiology Department. The telephone and fax number of the contact persons in the local department of Drug Safety and Epidemiology, specific to the site, are listed in the investigator folder provided to each site. The original copy of the SAE Report Form and the

fax confirmation sheet must be kept with the case report form documentation at the study site. Follow-up information should be provided using a new paper SAE Report Form stating that this is a follow-up to a previously reported SAE

Follow-up information provided must describe whether the event has resolved or continues, if and how it was treated, whether the treatment code was broken or not and whether the patient continued or withdrew from study participation. Each re-occurrence, complication, or progression of the original event must be reported as a follow-up to that event regardless of when it occurs.

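### Protocol Section 7.1 allows a life-threatening adverse event to be classed as non-serious, which contradicts the SAE definition in Section 7.2.1

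*Protocol*

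**What the plan says.** Protocol Section 7.1 lists what is recorded for each adverse event. Severity has three grades, of which the highest is "severe: prevents normal activities". Directly below the grades comes the statement at issue: "There may be cases where a severe AE that is life-threatening may not necessarily be an SAE". Its example, in parentheses, is "certain laboratory abnormalities in the absence of meeting other seriousness criteria". Further down the same list, the investigator records whether the event is serious and is referred to Section 7.2 for the definition.

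Protocol Section 7.2.1 defines an SAE as an adverse event "which meets any one of the following criteria". The first criterion is that it "is fatal or life-threatening". The section then explains that life-threatening, for this purpose, "refers to a reaction in which the patient was at risk of death at the time of the reaction", and it excludes threats that are only hypothetical. A separate criterion covers an event that "is medically significant, e.g. defined as an event that jeopardizes the patient or may require medical or surgical intervention".

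Protocol Section 7.2.2 requires that every SAE "must be reported to Novartis within 24 hours of learning of its occurrence". The SAP, under Adverse events, plans a table of serious adverse events by system organ class and preferred term.

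**The concern.** The two sections give different answers to the same question: is an adverse event that threatens life serious on that ground alone? Section 7.2.1 says yes. Section 7.1 says not necessarily.

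The example in Section 7.1 makes this more than a point of style. Renal injury and hypocalcemia are named risks of the drug in Protocol Sections 3.6 and 5.1.2, and both are detected largely through laboratory values. The exception therefore falls on a kind of event that this trial particularly needs to classify correctly. Three things follow from the serious label: the 24-hour report, possible handling as a SUSAR (both in Section 7.2.2), and entry in the SAP's SAE table.

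**Working it through.** No arithmetic applies, because the point rests on no figure. The check sets the texts side by side.

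1. **Is life-threatening sufficient under Section 7.2.1?** Yes. One criterion is enough ("which meets any one of the following criteria"), and life-threatening is among them. No further criterion is needed.

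2. **Is it sufficient under Section 7.1?** No. The example concerns abnormalities "certain laboratory abnormalities in the absence of meeting other seriousness criteria". The word *other* counts life-threatening as one seriousness criterion and then says that it does not suffice by itself. The example is introduced as an illustration, so the exception is not confined to laboratory findings.

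3. **Could Section 7.1 be using the word as a severity grade?** The scale stops at severe, defined by its effect on normal activities. It has no life-threatening grade, so the word has no separate severity meaning to fall back on.

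4. **Could Section 7.1 mean only hypothetical threats?** Section 7.2.1 does exclude those, and with that limit the two sections would agree. But Section 7.1 neither states the limit nor refers to it.

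5. **What is lost if a site applies the exception?**

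| Item | Effect of a non-serious classification |
|---|---|
| 24-hour report (Protocol 7.2.2) | Not required |
| SUSAR assessment (Protocol 7.2.2) | Not triggered, since it presupposes seriousness |
| SAE table (SAP, Adverse events) | Event absent |
| AE record and overall AE tables, treatment period | Event still present |
| Renal and hypocalcaemia analyses (SAP) | Event still retrieved, by preferred term or by central laboratory calcium |
| Newly occurring notable laboratory abnormalities (SAP) | Still tabulated |

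6. **Outside the treatment period the label matters more.** Section 7.1 ends the AE period at the end-of-study visit, while Section 7.2.2 requires SAE reports for 30 days beyond the last visit. A non-serious event after that visit, even one thought to be related, goes only into the investigator's source documents. Before the first infusion, a non-serious event is recorded as medical history in a randomized patient (Section 7.1) and only in source data in a screening failure (Section 6.1).

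**The case against.** The strongest reply is that Section 7.1 itself defers to Section 7.2. The pointer stands a few lines below the disputed sentence, a second pointer follows under hospitalization, and the 24-hour rule is tied to the SAE as Section 7.2 defines it. On this view the sentence only separates severity from seriousness, and its example is a value that looks alarming on paper in a child who is in no immediate danger. Section 7.2.1 also has a backstop, since an event that jeopardizes the patient is serious under the medically significant criterion.

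Much of this stands. There is textual support for treating Section 7.2 as governing, and a careful investigator would probably reach the right classification. The reply does not remove the conflict, however. The pointer sits in the same list as a sentence announcing an exception to the definition it points to, and no text says which prevails. The benign reading has to be supplied by the reader. The backstop rests on judgment, whereas the life-threatening criterion is meant to apply without it.

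A reader might go further and infer that such events would escape the DMC. The documents do not support that: Protocol Section 8.4 has the DMC review emerging safety signals and does not limit it to SAEs. Appendix 1 adds that the sponsor can see laboratory results once they have been sent to investigators.

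**Conclusion.** The sentence in Section 7.1 is incorrect when set against the protocol's own SAE definition, and the two sections must be reconciled. The consequence is narrow. A site that relies on Section 7.1 could omit an SAE report, and the event would be missing from the SAE table. Outside the treatment period it could also be missing from the AE data. Within the treatment period it would remain in the AE data and in the renal and calcium analyses.

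This rests on one assumption: that some sites would act on the exception as written and not follow the pointer to Section 7.2. The documents do not show how likely that is.

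It is tempting to add that, with approximately 46 patients per group, one or two misclassified events would visibly alter the SAE comparison. The documents give neither an expected SAE rate nor a frequency of life-threatening laboratory events, so no size can be attached to the effect. The severity is minor.

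**What to change.** Delete the sentence in Protocol Section 7.1, or replace it with: *A severe AE is not necessarily serious; any AE that is life-threatening as defined in Section 7.2.1 is an SAE.* The replacement keeps the legitimate distinction between severity and seriousness and brings in the definition already given in Section 7.2.1.

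The cost is one sentence in the next amendment, or a clarification letter to investigators in the meantime. No assessment, treatment or analysis changes, and the SAP needs no edit.
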